During the Phase 1b and Phase 2a 50 mg daily portions of the study, blood samples will be collected for PK analyses on Study Day 1 (predose, 1, 2, 4, 8, and 24 hours postdose), Day 14 (predose, 1, 2, 4, and 24 hours postdose), and predose on Days 7, 21, and 28. Additional samples will be collected predose at every monthly visit thereafter up to and including the Month 6 visit for those subjects who continue dosing.

In the Phase 2a portion of the study, approximately 70 subjects (5 in each alternative dosing schedule and 15 subjects in the 50 mg daily dosing schedule and 50 subjects in the SILK cohort) will have blood samples drawn for PK analyses.

For subjects receiving 150 mg of KD019 on Monday, Wednesday, and Friday: Samples will be collected on Study Day 1 (predose, and 1, 2, 4, 8, and 24 hours postdose); predose on Days 3, 5, and 8; and on Day 12 (predose, and 1, 2, 4, and 24 hours postdose).

For subjects receiving 150 mg of KD019 on Monday and Thursday: Samples will be collected on Study Day 1 (predose, and 1, 2, 4, 8, and 24 hours postdose); predose on Days 8, 11, and 18; and on Day 25 (predose, and 1, 2, 4, 8, and 24 hours postdose).

For subjects receiving 50 mg of KD019 daily:

Samples will be collected on Study Day 1 (predose, 1, 2, 4, 8, and 24 hours postdose), Day 14 (predose, 1, 2, 4, and 24 hours postdose), and predose on Days 7, 21, and 28. Additional samples will be

collected predose at every monthly visit thereafter up to and including the Month 6 visit for those subjects who continue treatment (Follow-Up Treatment Period).

For subjects receiving 50 mg of tesevatinib daily (the SILK cohort): Samples will be collected on Study Day 1 (predose, 1, 2, 4, and 8 hours postdose), Day 14 (predose, 1, 2, 4, and 8 hours postdose), and predose on Days 7, 21, and 28. Additional samples will be collected predose at every monthly visit thereafter up to and including the Month 6 visit.

In addition, blood samples for PK analyses will be collected if the QTc(F) interval increases by > 60 msec above average predose value (average of Day 1 predose and screening values) or to the level of ≥ 480 msec.

Exploratory Efficacy

In the Phase 2a Cohort:

- Evaluate the 6-month annualized change in GFR.
- Evaluate the annualized change from baseline in the reciprocal of serum creatinine

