	Screening		Early	Treatment 1	Period ^b		Drug Holiday Period	Month 2	Monthly Follow-Up Treatment Period ^c	End of Study ^d
Assessments	(-28 Days)	Day 1	Day 7 (±1 day)	Day 14 (±1 day)	Day 21 (±1 day)	Day 28 (±1 day)	4 Weekly Visits Beginning at Day 28 Visit (± 1 day)	4 Weekly Visits Beginning at Month 2 Visit (± 1 day)	Every 28 Days Beginning at Month 3 (± 3 days)	(30 Days from Last Dose) (± 3 days)
Informed consent	X							, ,		
Medical and PKD history (including genotype, if available)	X									
Physical examination (including weight) ^e	X	X	X	X	X	X		X°	X	X
Vital signs ^t	X	X	X	X	X	X		X°	X	X
Supine 12-Lead ECG ^g	X	X	X	X	X	X		X°	X	X
Clinical laboratory tests ^h	X	X	X	X	X	X	X	X°	X	X
Ocular evaluation	X								X	
Echocardiogram ^J	X					X			X	X
Pregnancy test ^k	X	X				X				X
MRI	X									X
Study drug administration		X X	X	X	X	X			X	
Concomitant medications ^p	X	X	X	X	X	X	X	X	X	X

Table 4-1: Schedule of Events for Subjects Enrolled in the Safety in Larger Kidneys (SILK) 50 mg Daily Portion of the Study

	Screening		Early	Treatm	ent Pe	eriod ^b		Drug Holiday Period	Month 2	Monthly Follow-Up Treatment Period ^c	End of Study ^d
Assessments	(-28 Days)	Day 1	Day 7 (±1 day)	Day (±1 da		Day 21 (±1 day)	Day 28 (±1 day)	4 Weekly Visits Beginning at Day 28 Visit (± 1 day)	4 Weekly Visits Beginning at Month 2 Visit (± 1 day)	Every 28 Days Beginning at Month 3 (± 3 days)	(30 Days from Last Dose) (± 3 days)
Adverse events ^p		To b	e collected j	from the	time i	nformed co	nsent signed	l until 30 days aft	ter last dose of s	tudy drug.	
PK sampling ^m		X	X	 	X	X	X		X°		
Plasma concentration								X	X		
Dispense/Collect study drug		X	X	X	X	X	X			X°	X

- a. Screening evaluations may be combined with Day 1 pre-treatment laboratory evaluations if both are done within 4 days before first dose of study drug.
- b. All protocol-specified clinic visits during the Treatment Period should occur within ± 1 day of the nominal visit day unless otherwise specified.
- c. Follow-up Treatment Period visits to be performed monthly (every 28 ± 1 day). For those subjects continuing on study beyond 12 months, visits will occur every 2 months \pm 3 days.
- d. End-of-Study visit is to be performed 30 days (± 3 days) after last dose of study drug.

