- j. Echocardiograms are to be obtained at Screening, on Day 28, and at Months 3, 6 every 6 months thereafter, and End-of-Study visits and are to include measurement of ejection fraction and assessment for pericardial effusion and valvular abnormalities. Note: If subject has had echocardiogram within 2 months of End-of-Study visit, there is no need to obtain echocardiogram at End of Study visit. For those subjects who have already had their Month 12 visit, this may be performed at Month 13 and then subsequent echocardiograms may be performed on the same schedule as the MRIs. If pericardial effusion is diagnosed via echocardiogram, subject should be rechecked within 1–3 months to monitor for progression.
- k. Pregnancy tests will be done using urine samples in women of childbearing potential. Subjects must have a negative urine pregnancy test documented within the 24-hour period prior to the first dose of study drug. Pregnancy tests are to be performed at Screening, predose on Day 1, Day 28, Month 3 (and every 3 months thereafter), and End-of-Study visits only. Confirm with serum testing if urine sample is positive.
- 1. Screening MRI will be performed after informed consent form has been signed and prior to other screening assessments. MRI to be performed at Month 6 and then every 6 months thereafter. Note: If subject has had MRI within 3 months of End of Study visit, there is no need to obtain MRI at End-of-Study visit.
- m. Blood samples will be collected for PK analyses on Study Day 1 (predose, 1, 2, 4, and 8 hours postdose), Day 14 (predose, 1, 2, 4, and 8 hours postdose), and predose on Days 7, 21, and 28. PK samples will also be drawn if the QTc(F) interval increases by > 60 msec above average baseline or to the level of

- \geq 480 msec (see Section 11.3.3).
- n. PK samples will be collected predose at every monthly visit up to and including Month 6 visit.
- o. These assessments are to be performed ONLY at the Month 2 visit, not at the 3 weekly visits which follow during the Month 2 period.
- p. Blood draws during the drug holiday or Month 2 visits may be performed by a visiting nurse at the subject's home; if the subject chooses this option, the study team should call the subject on the same day of the visit to inquire about concomitant medications and AEs.

Table 4-2: Schedule of Events for Subjects Enrolled in Phase 1b and Phase 2a 50 mg Daily Portions of the Study

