- d. Clinical laboratory tests consist of hematology, serum chemistry panel, coagulation, TSH, and urinalysis (see Section 9.9 for a complete list of assessments). TSH levels will be evaluated at Screening and then every 3 months. (Need not be repeated if screening visit occurred within 4 days prior to Day 1 visit.)

 Ocular evaluations are to be performed at Screening and at Months 3, 6, 9, 12, 18, and 24. The following assessments should be performed: evaluation of best corrected visual acuity, slit lamp photography of the iris, non-mydriatic photography of retina within the arcade, pils, and optical coherence tomography (OCT) of the optic nerve head and macula.
- f. Pregnancy tests will be done using urine samples in women of childbearing potential. To be performed at screening, predose on Day 1, Day 28, Month 3 (and every 3 months thereafter), and End-of-Study visits only. Confirm with serum testing if urine sample is positive.
- g. In the Phase 1b and Phase 2a 50 mg daily portions of the study, blood samples will be collected for PK analyses on Study Day 1 (predose, 1, 2, 4, 8, and 24 hours postdose), Day 14 (predose, 1, 2, 4, and 24 hours postdose), and predose on Days 7, 21, and 28. PK samples will also be drawn if the QTc(F) interval increases by > 60 msec above average baseline or to the level of ≥ 480 msec (see Section 11.3.3).
- h. Screening must occur within 28 days of first dose of study drug. Screening evaluations may be combined with Day 1 pre-treatment laboratory evaluations if both are done within 4 days before first dose of study drug.
- i. All protocol-specified clinic visits during the Treatment Period should occur within ± 1 day of the nominal visit day unless otherwise specified.

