- j. Follow-up Treatment Period visits to be performed monthly (every 28 ± 3 days). These visits are only for those subjects who are continuing on study treatment beyond the initial 28-day Early Treatment Period. For those subjects continuing on study beyond 12 months, visits will occur every 2 months ± 3 days. Now that the MTD for daily dosing has been established, if it results in a dose increase for subjects not already receiving the MTD, the study assessments required for the monthly follow-up visits (ie, PK and postdose ECG and vital sign measurements not required) should be performed on Days 1 and 14 of the first month, then monthly for a total of 6 months, then every 2 months thereafter. The same schedule of evaluation will apply to any subjects increased from 50 mg/day to 100 mg/day after 6 months of treatment at 50 mg/day and after the 100 mg dose group is determined not to be a DLT dose cohort. Section 9.6 for study assessments to be performed and the timing of visits.
- k. End-of-Study visit is to be performed 30 days (± 3 days) after last dose of study drug.
- 1. Echocardiograms are to be obtained at Screening, on Day 28, and at Months 3, 6 every 6 months thereafter, and End-of-Study visit and are to include measurement of ejection fraction and assessment for pericardial effusion. Note: If subject has had echocardiogram within 2 months of End-of-Study visit, no need to obtain echocardiogram at End of Study visit. For those subjects who have already had their Month 12 visit, this may be performed at Month 13 and then subsequent echocardiograms may be performed on the same schedule as the MRIs. If pericardial effusion is diagnosed via echocardiogram, subject should be rechecked within 1–3 months to monitor for progression.
- m. Screening MRI should be performed following informed consent and prior to other Screening assessments. Results must be reviewed before the first dose of study drug is administered. MRI to be performed at Month 6 and then every 6 months thereafter. Note: If subject has had MRI within 3 months of End of Study visit, there is no need to obtain MRI at End-of-Study visit.
- n. Subjects on the Phase 1b portion of the study will have study drug held for a one-time drug holiday of at least 14 and up to 28 days with creatinine and cystatin C measurements performed before and immediately after the drug holiday, as well as a predose PK sample prior to restarting study drug.

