- b. Vital sign measurements consist of sitting blood pressure, pulse rate, respiratory rate, and oral or tympanic temperature. On Day 1, measurements should be performed predose and 1 and 4 hours postdose. See Section 9 for appropriate blood pressure measuring technique. For subjects participating in PK, vital signs are also to be measured 8 hours postdose on Day 1.
- c. Supine 12-Lead ECGs will be performed at Screening, predose, and 1 and 4 hours postdose on Days 1 and 12; predose on Day 26 and Day 1 of Months 2 and beyond; and at End-of-Study visit (repeat 3 times consecutively within 30 minutes [must have an interval of at least 1-2 minutes between ECGs]). If QTc(F) is prolonged to > 60 msec above baseline at any evaluation or to the level of ≥ 480 msec, refer to Section 11.3.3.1 for procedure to be followed. For subjects participating in PK, ECGs are also to be performed 8 hours postdose on Day 1.
- d. Clinical laboratory tests consist of hematology, serum chemistry panel, coagulation, and urinalysis (see Section 9.9 for a complete list of assessments).
- e. Ocular evaluations are to be performed at Screening and at Months 3, 6, 9, 12, 18, and 24. The following assessments should be performed: evaluation of best corrected visual acuity, fundoscopic exam with non-dilated pupils, slit lamp photography of the iris, non-mydriatic photography of retina within the arcade, pils, and optical coherence tomography (OCT) of the optic nerve head and macula.
- f. Optional; to be conducted at selected sites in 3–7 subjects. Second time point should be done on Day 12, 13, 14 or 15, and all study related procedures required on Day 12 may be done at this visit. Based upon the results of testing, a third timepoint may be performed within the first 2 months of study drug dosing and after consultation with the medical monitor.
- g. Urine pregnancy tests are to be done in women of childbearing potential at Screening, predose on Day 1, Day 26, at Month 3 (and every 3 months thereafter up through Month 12), and End-of-Study visits only. For subjects continuing on study past 12 months who have visits every 2 months, testing should be done every 2 months to coincide with their visit schedule. Confirm with serum testing if urine sample is positive.
- h. Subjects will start Phase 2a with an alternative dosing schedule of 150 mg of KD019 on Monday, Wednesday, and Friday of each week.

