- e. Ocular evaluations are to be performed at Screening and at Months 3, 6, 9, 12, 18, and 24. The following assessments should be performed: evaluation of best corrected visual acuity, slit lamp photography of the iris, non-mydriatic photography of retina within the arcade, pils, and optical coherence tomography (OCT) of the optic nerve head and macula.
- f. Optional; to be conducted at selected sites in 3–7 subjects. Second time point should be done between Day 22 and 25 and all study related procedures required on Day 25 may be done at this visit. Based upon the results of testing, a third timepoint may be performed within the first 2 months of study drug dosing and after consultation with the medical monitor.
- g. Urine pregnancy tests are to be done in women of childbearing potential at Screening, predose Day 1, Day 25, at Month 3 (and every 3 months through Month 12), and End-of-Study visits only. For subjects continuing on study past 12 months who have visits every 2 months, testing should be done every 2 months to coincide with their visit schedule. Confirm with serum testing if urine sample is positive.
- h. Subjects will start Phase 2a with an alternative dosing schedule of 150 mg on Monday and Thursday of each week.
- i. In the Monday/Thursday dosing schedule of the Phase 2a portion of the study, approximately 5 subjects will have blood samples drawn for PK analyses. If accrual goals have nearly been met, only those who can undergo iothalamate or PK testing will be enrolled. Blood will be collected on Study Day 1 (predose, and 1, 2, 4, 8, and 24 hours postdose); predose on Days 8, 11, and 18; and on Day 25 (predose, and 1, 2, 4, 8, and 24 hours postdose), and predose at every monthly visit thereafter (up to and including the Month 6 visit) (Subjects undergoing iothalamate testing will not undergo PK sampling.) Also, collect PK sample if QTc(F) interval increases by > 60 msec above average baseline or to the level of ≥ 480 msec (see Section 11.3.3.1).
- j. Screening must occur within 28 days of first dose of study drug. Screening evaluations may be combined with Day 1 pre-treatment laboratory evaluations if both are done within 4 days before first dose of study drug. Results must be reviewed before the first dose of study drug is administered.
- k. All protocol-specified clinic visits during the Treatment Period should occur within ± 1 day of the nominal visit day unless otherwise specified.

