9.6 Phase 1b and 2a Subjects Continuing KD019 beyond 12 Months

For subjects continuing to receive study drug beyond 12 months, the following safety assessments should be performed every 2 months (\pm 3 days):

- Limited physical examination, including weight (See Section 9 of protocol for a listing of systems to be examined/reviewed)
- Vital sign measurements
- Supine 12-Lead ECG (to be performed predose prior to collection of any blood samples) (repeat 3 times consecutively within 30 minutes [must have an interval of at least 2 minutes between ECGs])

Note: If QTc(F) is > 60 msec above highest average predose reading (average of baseline and screening) or to the level of ≥ 480 msec, refer to Section 11.3.3. This should be done based upon the local site analysis.

- Clinical laboratory tests by central laboratory
- Pregnancy test (urine) for women of childbearing potential (if positive, perform serum pregnancy test)
- Perform drug accountability and dispense adequate supply of study drug
- Study drug administration
- Concomitant medications
- Adverse event assessment

The following safety assessments should be performed every 6 months:

• Echocardiogram (for those subjects who have already had their Month 12 visit, this may be performed at Month 13 and then subsequent echocardiograms may be performed on the same schedule as the MRIs)

Note: If pericardial effusion is diagnosed via echocardiogram, subject should be rechecked within 1–3 months to monitor for progression.

MRI

For Phase 1b subjects experiencing a dose increase from 50 mg to 100 mg, now that the MTD for daily dosing has been established: The study assessments in Section 9.6 (above) should be performed as follows:

- Days 1 and 14 of the first month, then monthly for a total of 6 months
- Every 2 months thereafter
 An echocardiogram and MRI should still be performed every 6 months

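### After Month 12, Tables 4-1 (SILK) and 4-2 keep pregnancy tests at every 3 months, while Section 9.6 and Tables 4-3 and 4-4 require every 2 months; Table 4-1 has no pointer to Section 9.6

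*Protocol*

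**What the plan says.** Four schedule tables and one body section of the protocol bear on pregnancy testing after Month 12.

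- **Table 4-1 (SILK), footnote k.** After Screening and Day 1, tests fall at "Day 28, Month 3 (and every 3 months thereafter), and End-of-Study visits only". Nothing ends or alters the 3-month rule at Month 12.
- **Table 4-2 (Phase 1b and Phase 2a 50 mg daily), footnote f.** The same rule: "Month 3 (and every 3 months thereafter), and End-of-Study visits only".
- **Section 9.6.** For Phase 1b and 2a subjects still on drug past 12 months, "the following safety assessments should be performed every 2 months". The urine pregnancy test is on that list.
- **Tables 4-3 and 4-4, footnote g.** The 3-month rule stops at Month 12; Table 4-4 puts it as "at Month 3 (and every 3 months through Month 12), and End-of-Study visits only". For subjects who continue past that point, both footnotes say "testing should be done every 2 months to coincide with their visit schedule".
- **Visit interval.** Table 4-1 footnote c: "For those subjects continuing on study beyond 12 months, visits will occur every 2 months", with a window of 3 days either way. Table 4-2 footnote j gives the same interval.
- **Pointers to Section 9.6.** Table 4-2 footnote j refers the reader to "Section 9.6 for study assessments to be performed and the timing of visits", and the visit footnotes of Tables 4-3 and 4-4 (l and m) also refer there. No footnote of Table 4-1 does.

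**The concern.** A site running SILK from Table 4-1 would apply a different safety-monitoring rule from a site running it from Section 9.6. The closing word *only* in footnotes k and f means they cannot be read as a minimum that Section 9.6 then adds to. The 3-month rule also does not fit a 2-monthly visit plan, so a site that follows the footnote has due dates with no visit attached.

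Subjects must use two forms of contraception (inclusion criterion 10), so the test is a backstop. It still has a consequence: under Section 13.3.9 pregnancy takes the subject off study. A longer interval between tests delays detection and therefore delays stopping the drug.

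**Working it through.** The plan states no figure to reproduce. The check compares the texts and counts test dates.

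**1. Does Section 9.6 cover SILK?** Yes. Its heading names Phase 1b and 2a subjects and exempts no cohort. The Synopsis (Pharmacokinetics) lists, within the Phase 2a portion, "15 subjects in the 50 mg daily dosing schedule and 50 subjects in the SILK cohort". Section 14.2 gives 65 Phase 2a subjects at 50 mg daily, and 15 + 50 = 65. Section 7.2 provides treatment for 24 months in all cohorts, so Months 12 to 24 apply to SILK.

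**2. Does another section settle the matter?** No. Section 9.2.5.1 repeats the 3-month rule for SILK, but its heading limits it to Months 3–12. After that, Section 9.6 is the only body text on pregnancy testing at scheduled on-treatment visits.

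**3. Count from Month 12 to Month 24.** Assumption: 2-monthly visits are numbered from Month 12. The End-of-Study test is common to both rules and is left out.

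| Rule | Test months | Tests | Longest interval (months) |
|---|---|---|---|
| Section 9.6; Tables 4-3 and 4-4 | 14, 16, 18, 20, 22, 24 | 6 | 2 |
| Footnotes k and f, tested on time | 15, 18, 21, 24 | 4 | 3 |

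Difference: 6 − 4 = 2 tests per woman of childbearing potential.

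**4. Fit with the visits.** Visits fall at Months 14, 16, 18, 20, 22 and 24. Footnote due dates are Months 15, 18, 21 and 24. Only Months 18 and 24 coincide. Months 15 and 21 lie a month from the nearest visit, and a 3-day window does not bridge that. If visits fell on odd months instead, Months 18 and 24 would be the ones missed, so two of the four due dates are stranded either way.

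**5. If the stranded tests move to a neighbouring visit.** Month 15 goes to 14 or 16, and Month 21 to 20 or 22. Intervals are counted from the Month 12 test.

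| Test months | Intervals (months) | Longest |
|---|---|---|
| 14, 18, 20, 24 | 2, 4, 2, 4 | 4 |
| 14, 18, 22, 24 | 2, 4, 4, 2 | 4 |
| 16, 18, 20, 24 | 4, 2, 2, 4 | 4 |
| 16, 18, 22, 24 | 4, 2, 4, 2 | 4 |

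The longest interval is 4 months in every case. Keeping to 3 months needs extra visits at Months 15 and 21.

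**The case against.** The strongest reply concerns weight; the texts plainly differ.

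- **The protocol already accepts a 3-month interval.** All cohorts test 3-monthly up to Month 12, with the same drug and the same contraception requirement. The reason given for 2-monthly testing afterwards is to match the visits, and no risk specific to later months is named. This stands. On the texts as written, the rules differ by one month in interval.
- **The 4-month interval breaks both rules.** It arises only if a site moves the stranded tests and adds none; a site could instead test at every visit. This also stands, and the figure is conditional. But testing at every visit departs from footnote k, so a site cannot avoid the problem by following the footnote.
- **Table 4-2 is partly covered.** Its footnote j sends the reader to Section 9.6. That softens the conflict there without removing it, because footnote f still says *only*. Table 4-1 has no such pointer.
- **Suspected pregnancy need not wait.** Section 9.8 allows a test at an unscheduled visit. That helps when pregnancy is suspected, whereas a scheduled test is there for when it is not.
- **Few subjects may be affected, and no analysis changes.** Only women of childbearing potential still on drug past Month 12 are concerned, and their number is not stated. No endpoint, population or sample size depends on it. Both points stand, and they limit the grade of the finding. They do not reconcile the texts.

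**Conclusion.** The concern holds. After Month 12, Table 4-1 footnote k and Table 4-2 footnote f contradict Section 9.6, and footnote g of Tables 4-3 and 4-4 shows how the protocol meant testing to run once visits become 2-monthly. No reason is given for testing daily-dosed women less often.

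The size is 4 tests against 6 per woman of childbearing potential treated from Month 12 to Month 24. The longest interval is 3 months against 2, or 4 if the stranded tests are moved. The counts assume visits numbered from Month 12 and treatment through Month 24.

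This is an inconsistency in an operative safety schedule, most serious for SILK. It should be corrected, but it does not threaten the trial's statistical conclusions.

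**What to change.** In Table 4-1 footnote k and Table 4-2 footnote f, end the 3-month rule at Month 12. Then state for subjects continuing past that point, as Tables 4-3 and 4-4 already do, that "testing should be done every 2 months to coincide with their visit schedule". Add a pointer to Section 9.6 in Table 4-1; footnote c is the natural place. Section 9.2.5.1 needs no change, since it stops at Month 12.

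The cost is two footnote edits and one cross-reference in an amendment. Measured against the footnotes, this adds 2 urine tests per woman of childbearing potential over Months 12 to 24, all at visits already planned. Measured against Section 9.6, it adds none.
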